Study protocol

**Sealed Therapeutic Shoe vs. Total Contact Cast as Treatment of Diabetic
Foot Ulcers: a Multicenter RCT**

Clinical Trial Registration Number: Unique Protocol ID: 18RS6667

Date: 9 September 2019

Background

Approximately 19-34 % of all people with diabetes will at some time in life develop a diabetic foot ulcer (DFU).¹ People with diabetes are especially prone to develop foot ulcers because of different diabetic complications, especially angiopathy and peripheral neuropathy.

The DFUs are often hard to heal and the treatment is long-lasting. The DFUs result in lower physical and mental quality of life and affects social relationships.² The treatment is also very costly,^{1,3} it has been estimated that 25-50 % of diabetic inpatient care is related to DFUs.⁴ Despite extensive treatment, all DFUs do not heal but some end in amputation. People with diabetes are at a 25-fold risk of amputation and every 20 second a person somewhere in the world has the foot amputated because of diabetes.⁵ 85 % of these amputations are preceded by a foot ulcer⁶ and many of these ulcers and amputation could have been prevented.⁷

Total contact cast (TCC) as gold standard treatment of DFUs

Plantar DFUs often are the result of a combination of foot deformities that increase plantar pressures when the person walks and that the person keeps walking despite high pressure and ulcers because he or she has lost sensation in the feet because of sensory neuropathy. Literature reviews and international guidelines^{8,9} recommend non-removable knee-high offloading devices, for example, a total contact cast (TCC) to treat plantar DFUs, as this offloads the ulcer from mechanical loading all day and night. Still, TCC is not accepted by all patients and is contraindicated in a number of cases because of negative side-effects. Most of these side-effects are the consequences of immobilizing the ankle joint, which impairs gait and results in lower ambulatory activity. For example, side-effects include reduction of joint flexibility, weight gain, muscle atrophy, sick leave from work and social isolation.¹⁰ In addition, a TCC can give secondary ulcers why weekly visits to the hospital is necessary to change casts. For these reasons, TCC is only used for a minority of the patients for whom it could be beneficial, despite being the gold standard treatment.¹¹

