Participants in both groups will be assessed by a physiotherapist on five occasions (Figure 1): at base-line, four weeks into the treatment period, and then 1, 6 and 12 months after healing (when treatment is ended). For the 4 week into treatment and 1 month post-treatment assessments, a visit window of ± 1 week will be used. For the 6 and 12 months post-treatment assessments, a visit window of ± 1 month will be used. Standardized and validated instruments and assessment methods will be used for the data collection (Table 1).

Aim 1: Ulcer healing (primary end point)

Primary outcome measure is ulcer healing after 12 weeks of treatment, defined by the Food and Drug Administration (FDA) as full skin epithelization of the ulcer, confirmed by a second observation 14 days later.¹⁸ The cast technicians will assess ulcer healing in both the intervention group and control group. They will also photograph the ulcer and healed skin so a person blinded to group allocation can assess ulcer healing afterwards.

Aim 2: Adverse events during treatment (secondary end points)

Adverse events that are judged to be related to the offloading devices (shoe or TCC) will be classified as adverse device effects (ADE) and serious adverse device effects (SADE).³² ADE include, but are not limited to, skin abrasions, blisters, sleep disturbances, issues with gait and balance, etc. SADE include, but are not limited to, new foot ulcers that result in amputation (major amputation = above ankle, minor amputation = below ankle), sepsis, etc.

Adverse events that are not related to the offloading devices are classified as adverse events (AE) and serious adverse events (SAE).³² AE include, but are not limited to, skin abrasions, new foot ulcers on the contralateral foot and not related to the device, etc. SAE include, but are not limited to, death, amputation, onset of acute Charcot foot, sepsis, etc. (not related to the offloading device). However, in accordance with previous studies on this patient population, the investigators choose not to include all AE and SAE as the patient population suffers from multiple co-morbidities and therefore a high incidence of illness and hospital admissions unrelated to the DFU and offloading devices can be expected.³³ Therefore, all

ADE and SADE will be assessed, but only certain types of AE and SAE that are of particular interest, such as, amputation, death and onset of acute Charcot foot.

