2.7 TIMING OF OUTCOME ASSESSMENTS

Table 1 below lists outcomes and time points for assessments (base-line, 4 weeks into treatment, and 1, 6 and 12 months after treatment end). For the 4 week into treatment and 1 month post-treatment assessments, a visit window of ± 1 week will be used. For the 6 and 12 months post-treatment assessments, a visit window of ± 1 month will be used.

Table 1. Overview of variables and assessment methods.

Variable (scale level: nominal=N, ordinal=O, interval=I)	Assessment method	Assessment occasion				
		Treatment period		Follow-up after treatment end		
		Base- line	4 weeks	1 month	6 months	12 months
Ulcer healing (N)	Clinical observation + blinded photo	X	X	X		
Skin complications (N)	Clinical observation + blinded photo	X	X	X		
Glycemic control (I)	Blood sample (HbA1c) ^a	X	X	X	X	X
BMI (I)	Measurement of weight and height	X	X	X	X	X
Gait function (I)	10 meter walk test ^{b 17}	X	X	X	X	X
Gait function (I)	Timed up and go ^{b 18}	X	X	X	X	X
Balance (O)	Berg balance scale ^{b 19}	X	X	X	X	X
Muscle atrophy (I)	Calf circumference ^{a 20}	X	X	X	X	X
General quality of life (O)	RAND-36 ^{c 21} , EQ-5D-5L ^{c 22}	X	X	X	X	X
Disease-specific quality of life (O)	DFS-SF ^{c 23}	X	X	X	X	X
Physical activity (I)	ActivPAL ^{d 24}	X	X	X	X	X
Physical activity (O)	National Board of Health and Welfare's indicator questions ²⁵	X	X	X	X	X
Bone mass density (I)	DXA ^e (heel bone)	X		X	X	X
Locus of control (O)	Questions from MHLC-C ^{c 26}	X		X	X	X
Ankle range of motion (I)	Goniometer ^{a 27}	X		X	X	X
Ankle strength (I)	Dynamometer ^{a 28}	X		X	X	X
Adherence to therapeutic shoes (O)	Questions from Q-TFA ^{c 29}	X		X	X	X
Treatment satisfaction (O)	Visual analogue scale ^c		X	X		
New ulcers, amputations, death, Charcot foot (N)	Patient file and self-report ^c				X	X
Health care consumption (O) ^f	Patient administration systems and self-report ^c			X	X	X
Sick leave from work (I) ^f	Self-report, ^c Swedish Social Insurance Agency's system			X	X	X

^aStandardized method, ^bfunction test, ^cquestionnaire, ^dactivity monitor, ^eDual-energy X-ray absorptiometry ^ffor the of health-economic analysis.

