3.2 ADHERENCE AND PROTOCOL DEVIATIONS

Adherence to the interventions (sealed shoe and TCC) is defined as continuous use of the devices during the treatment period. If a person treated with TCC removes the device on one or more occasions or refuses to continue treatment this will be considered non-adherence. If a person treated with a sealed shoe removes the device (assessed by inspecting if the seal has been broken) on one or more occasions or refuses to continue treatment this will be considered non-adherence.

Non-adherence will be presented per type of non-adherence and frequency. All types of non-adherence will be presented as number and percentage. In addition, removal of devices will be presented as means and standard deviation.

A protocol deviation is defined as a failure to adhere to the protocol such as the wrong intervention being administered, incorrect data being collected and documented, errors in applying inclusion/exclusion criteria or missed follow-up visits. This will be presented as number and type, per study group.

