6 STATISTICAL ANALYSES

6.1 ANALYSIS METHODS

6.1.1 ANALYSIS OF THE PRIMARY EFFICACY ENDPOINT(S)

Primary efficacy endpoint is ulcer healing at 12 weeks, defined as complete epithelialization which is maintained for a minimum of 14 days (as required by the FDA).³¹ Healing is thus a single endpoint assessed on a nominal scale.

Ulcer healing will be assessed by the cast technician at the local hospital who redress the DFU, approximately 1-2 times per week (depending on the status of the DFU) in both groups. The cast technician will also photograph the DFU so it can be assessed by another person, blinded to group allocation.

In the analysis of the primary endpoint, the ITT dataset (analyzed with and without adjustment for covariates) and the per protocol dataset (analyzed without adjustment for covariates only) will be used. For the non-adjusted analyses, crude risk ratio (RR) or OR will be calculated to assess the impact of offloading device type on ulcer healing. For the adjusted analysis, baseline variables (sex, age, education level, living conditions, diabetes type and duration, glycemic control, BMI, history of previous foot ulcers and amputations, foot deformities, index foot ulcer characteristics, number of active ulcers, use of tobacco, peripheral artery disease, and neuropathy, see point 5.1) will be included as candidates in a logistic multiple regression, using backward selection and a p-value of 0.10 as cut-off for removal.

Participants for whom the 12 week observation is missing will be categorized as “not healed”. The statistician conducting the analysis will be blinded to group allocation.

The proportion of healed ulcers in each study group will be calculated, and the results will be presented as RR or OR and corresponding 95% CI.

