6.1.2 ANALYSIS OF THE SECONDARY ENDPOINT(S)

The secondary analyses are not dependent on the findings of the primary endpoint. No adjustment for Type 1 errors will be used as only one or a few statistical tests will be conducted for each secondary endpoint.

The secondary endpoints are time to healing and measures listed in Table 1. Each secondary endpoint is measured between one and five occasions during the study. The ITT dataset will be used for all analyses of secondary endpoints. Adjusted analyses will only be conducted for certain secondary endpoints that are of particular interest.

Time to healing will be compared between the study groups using survival analysis. Kaplan-Meier survival curves will be produced for the two study groups with median healing times and 95 % CI. Participants for whom the ulcer has not healed will be treated as censored and their date of trial exit or date of last available assessment will be used to calculate their duration in the trial. Hazard ratio with

95% CIs will be presented. Treatment effect will be explored using a Cox proportional hazards model including stratification factors (ulcer area and depth at baseline, periphery artery disease and infection grade) initially.

Survival analysis as above (but without adjustment) will also be used to compare ulcer recurrence after healing between the study groups. Recurrence rates at 12 months after healing will also be compared.

The analysis of the other secondary endpoints will be conducted according to scale level (nominal, ordinal or interval; Table 1) and compared at each time point (base-line, 4 weeks into treatment and 1, 6 and 12 months post-treatment) using the ITT dataset without adjustment for covariates: t-tests for ordinal and interval data if the assumptions of the t-test is fulfilled (normal distribution and equal variances), otherwise Wilcoxon rank sum test will be used. The Chi-squared test or generalized linear regression method will be used for nominal scale data. For each comparison both exact p-values and two-sided 95% CI will be reported.

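### The SAP's censoring rule for time to healing lets unhealed participants accrue up to about 11-12 months of risk time with no scheduled ulcer check, which can bias the hazard ratio in either direction

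*SAP*

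**What the plan says.** SAP 6.1.2 makes time to healing a secondary endpoint, analysed on the ITT dataset with Kaplan-Meier curves, a hazard ratio and a Cox model. Unhealed participants are censored, and "their date of trial exit or date of last available assessment will be used to calculate their duration in the trial".

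The passages that fix what those dates can be are:

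- **Ulcer checks on treatment.** The cast technician assesses the ulcer "approximately 1-2 times per week (depending on the status of the DFU) in both groups" (SAP 6.1.1).
- **Scheduled checks.** In SAP 2.7, Table 1, the ulcer-healing row is marked at baseline, 4 weeks and 1 month after treatment end, and not at 6 or 12 months.
- **Windows.** The 1-month check may fall up to a week either side of its due date. The later visits have more room: "For the 6 and 12 months post-treatment assessments, a visit window of ± 1 month will be used" (SAP 2.7).
- **Leaving treatment.** A TCC participant is non-adherent if he or she "removes the device on one or more occasions or refuses to continue treatment" (SAP 3.2), with a parallel rule for the shoe. SAP 4.4 lists refusing treatment and refusing follow-up as alternatives, so one can happen without the other.
- **Follow-up clock.** The Protocol (Data collection) times the later visits "and then 1, 6 and 12 months after healing (when treatment is ended". It does not say what starts the clock for someone who never heals.

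**The concern.** A participant should count as at risk of an observed healing only while healing could be observed. The first permitted date, trial exit, can fall long after the last look at the ulcer. The second is no safer as worded, because a physiotherapist or questionnaire visit would qualify. Two analysts could both follow the SAP and report different hazard ratios from the same data.

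Those affected are participants who stop the device unhealed and remain in follow-up. They stay in later risk sets as unhealed, and any healing after the last check goes unrecorded. An arm with more such participants appears to heal more slowly. At stake are the hazard ratio and the healing curves for this secondary endpoint.

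**Working it through.** The documents give no event number, hazard ratio or power for time to healing, so there is no figure of the plan's own to reproduce.

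**Step 1: length of the gap** (SAP 2.7; 1 month taken as 4.35 weeks).

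- From the 1-month check to a 12-month exit: 12 - 1 = 11 months, or 11 × 4.35 ≈ 48 weeks.
- With both windows at their limits: 48 - 1 - 4.35 ≈ 42 weeks to 48 + 1 + 4.35 ≈ 53 weeks.
- If the 1-month check is missed: 12 months (52 weeks), at most 13 months (57 weeks).
- For someone who leaves the trial while still on treatment, the gap is about a week or less.

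**Step 2: share of participants affected.** The input from the plan is 90% healed at 12 weeks in both arms (SAP 2.3). Assumptions: exponential healing; 5% (shoe) and 20% (TCC) assigned a stop, uniform over weeks 0-6; healing rate unchanged after the stop.

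- Weekly rate: λ = -ln(0.1)/12 = 0.192.
- Mean probability of being unhealed at the stop: (1 - e^(-6λ))/(6λ) = 0.684/1.151 = 0.594.
- Stopped unhealed: TCC 0.20 × 0.594 = 11.9%; shoe 0.05 × 0.594 = 3.0%. Among 56 per arm that is about 6.7 and 1.7 people.
- Still unhealed at a check 4.35 weeks later: multiply by e^(-4.35λ) = 0.434, giving 5.2% and 1.3%.
- Still unhealed if followed to week 12: 0.20 × 0.10 = 2.0% and 0.05 × 0.10 = 0.5%.

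**Step 3: hazard ratio under trial-exit censoring.** Simulated Cox models, true HR 1.00, shoe against TCC, so a value above 1 favours the shoe. Exit is about 12 months after the stop.

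| Last ulcer check | Unhealed at that check, TCC / shoe (stops in weeks 0-6) | HR, stops in weeks 0-6 | HR, stops in weeks 0-12 |
|---|---|---|---|
| At the stop | 11.9% / 3.0% | 1.22-1.26 | 1.18 |
| 1 month after the stop | 5.2% / 1.3% | 1.09 | 1.07 |
| Week 12 | 2.0% / 0.5% | 1.02 | not run |

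The range in the first row comes from separate runs with slightly different set-ups. Under these assumptions, censoring at the last ulcer check returns the true value to within about 0.02.

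**Step 4: other settings.** Stops are in weeks 0-12. The main figure has the last check at the stop; the figure in brackets has it at the 1-month visit.

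- Equal stopping, true HR 1.00: 1.00 (1.00).
- Rates reversed, 20% shoe and 5% TCC, true HR 1.00: 0.85 (0.93).
- Only 70% healed at 12 weeks, true HR 1.00: 1.26 (1.15) with more stopping under TCC; 0.80 (0.87) with more under the shoe.
- True HR 0.80, equal stopping of 10% or 20%: 0.83 (0.82) or 0.85 (0.82).
- Kaplan-Meier healing at 12 weeks, last check at the stop: mean unhealed at the stop is 0.9/2.303 = 0.391. With 20% stopping the curve reads 0.90 - 0.20 × (0.391 - 0.10) = 0.84; with 10% it reads 0.87. This occurs even when the arms are balanced.

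**Step 5: scale against sampling error.** With 112 participants there are about 0.9 × 112 ≈ 101 healings. The SE of log HR is about √(4/101) = 0.20, a 95% CI factor of e^(1.96 × 0.199) ≈ 1.48. A bias of 1.02, 1.09 or 1.26 is ln(HR)/0.199 ≈ 0.1, 0.4 or 1.2 standard errors.

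**Step 6: if healing slows after the stop** (5% against 20%, stops in weeks 0-6, 1-month check attended). The target is the fully observed ITT hazard ratio.

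| Healing rate after the stop | ITT target | Censored at last check | Censored at trial exit |
|---|---|---|---|
| One quarter | 1.13-1.15 | 1.04-1.05 | 1.18-1.19 |
| Zero | 1.23 | 1.07 | 1.23 |

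**The case against.** The strongest reply is that neither date is right in every case. The Protocol's background describes the removable devices used when TCC is not tolerated as not very effective, so healing may well slow after a stop. Censoring at the last check is then informative and pulls the ITT hazard ratio towards 1; in Step 6 trial exit is as close to the target or closer. Counting stoppers as unhealed would also match the primary rule in SAP 6.1.1, where a missing 12-week observation is a failure. This stands, and it shapes the fix. It does not rescue a rule with two interchangeable dates. If stoppers are meant to count as unhealed, the SAP should say so for this endpoint.

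Second, the larger hazard ratios require that nobody looks at the ulcer after the stop, whereas the plan has a 1-month check and a 12-week primary observation. This also stands, so 1.02-1.09 is the fairer range when those visits are attended.

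Third, the time may not be truly unobserved. Table 1 does not list the weekly or 12-week checks either, so its marks are not a complete record of when ulcers are seen. The Protocol names patient files as a source under Aim 3, where time to healing is listed. Neither document says, however, that index-ulcer healing dates will be taken from those files.

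A reader might infer that the bias will favour the shoe, because "TCC is not accepted by all patients". That sentence describes routine care. Trial participants have agreed to randomisation, and the documents give no stopping rate for either arm. Reversing the rates reverses the bias.

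**Conclusion.** The point holds as an ambiguity in a secondary analysis that can bias the hazard ratio. The wording permits trial exit, or a visit without an ulcer check, as the censoring date, and the schedule allows about 11-12 months between the last planned healing check and exit.

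The size rests on assumed stopping rates. At 5% against 20%, with no true difference, 90% healing and unchanged healing after the stop, the bias is about 1.02-1.09 if the 12-week or 1-month check is attended and up to about 1.2-1.26 if no check follows. It is larger if fewer ulcers heal (1.15 with the 1-month check at 70% healing). It vanishes with equal stopping and no true difference, and its direction follows whichever arm stops more. A 12-month exit for an unhealed participant is itself an inference, since the Protocol starts that clock at healing.

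Two further readings are not supported. The primary non-inferiority test does not use this rule and is unaffected. The recurrence analysis has no demonstrated defect, because new ulcers are collected at 6 and 12 months from patient files and self-report.

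**What to change.** In SAP 6.1.2, delete trial exit as a censoring date and replace the sentence with, for example: *Participants whose ulcer has not been observed to heal are censored at the last date on which the index ulcer was examined or photographed and found unhealed.* If patient-file entries are to count, add that a documented unhealed status in the file also sets the date, and that healing dates found there count as events. State what starts the post-treatment clock for participants who stop unhealed.

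Add one sensitivity analysis that keeps treatment stoppers as unhealed to the end of follow-up, parallel to the primary rule, and report it beside the main result.

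The cost is a few sentences and one extra model. The cast technician already documents and photographs the ulcer at each visit, so no new data collection is needed unless patient-file dates are to be extracted. The downside is somewhat shorter follow-up for stoppers and, if healing slows once the device is off, informative censoring that can understate an ITT difference. The sensitivity analysis is there to show how much that matters.

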The participants will be randomized to treatment with sealed therapeutic shoe or TCC. The randomization will be stratified for ulcer size (smaller or bigger than 1 cm^2 , ulcer size calculated as longest diameter*longest perpendicular diameter) and study center, and use random permuted blocks of randomly varying size.

Recruitment of participants

People who fulfill the inclusion criteria and not the exclusion criteria will be given oral and written study information and asked about whether they are interested in participating in the study. Those who agree will sign an informed constant to participate.

Intervention group, sealed therapeutic shoe: A prosthetist/orthotist will try out new therapeutic shoes to the participants and make individual insoles after casts of the feet. There will a limited number of shoe types to choose between and the procedure and material for the insole production will be standardized. The ulcer will be offloaded by adjusting the insoles with the help of plantar pressure measurement using the F-scan system (Tekscan, Boston, MA, USA). The “seal” of the shoe consists of a soft plastic strip (Bracelok, DJO Nordic, Malmö) that have to be broken to remove the shoe.

[figure not shown]
Control group, TCC: The participants will be treated with TCC, applied in a standardized manner. Participants in this group will also receive shoes and insoles, according to the same protocol as above, before TCC treatment is initiated to be comparable to the other group in the long-term follow-up after healing, when both groups will use shoes and insoles to prevent reulceration.

Both groups will visit the cast technician 1-2 times/per week depending on the status of the ulcer. The cast technician will change dressings, note whether the seal has been broken (for the intervention group), change casts (for the control group), photograph and document ulcers and complications, and ask participants if they have experienced any issues with the treatment. After this, a new dressing is applied, and the shoe is sealed (intervention group) or

a new cast is applied (control group). Participants will use a cover on the shoe or cast while taking a shower, and for the intervention group a cover will also be used when sleeping. Both groups will receive written information about potential complications and contact information to the clinics.

Data collection

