2.2 RANDOMIZATION

The randomization will be stratified for study site and ulcer area (smaller or bigger than 1 cm², ulcer size calculated as longest diameter*longest perpendicular diameter) and use random permuted blocks of randomly varying size. The randomization details are stored on a protected server of Region Örebro County and cannot be accessed by those who provide clinical input to the SAP.

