2.3 SAMPLE SIZE

The sample size calculation was performed using <http://powerandsamplesize.com/Calculators/Compare-2-Proportions/2-Sample-Non-Inferiority-or-Superiority>. Primary outcome is proportion of healed ulcers after 12 weeks of treatment. Based on the literature and our feasibility study the proportion of healed ulcers after 12 weeks treatment is estimated to 90% with sealed shoe or TCC.^{15, 16} If accepting $p=0.05$, a statistical power of 80% and a non-inferiority limit of 10%, 112 participants are

needed. To compensate for attrition of participants during the long-term follow up of secondary outcomes, the aim is to recruit 150 participants. The participants will be randomized to treatment with sealed therapeutic shoe or TCC. However, if it turns out that it is too difficult to recruit 150 participants, the recruitment of participant will end when the primary end point (healing at 12 weeks) has been observed for 56 participants per group, giving a total of 112 which fulfils the sample size calculation.

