5 STUDY ASSESSMENTS

5.1 BASELINE PATIENT CHARACTERISTICS

Baseline characteristics that will be summarized include: sex, age, education level, living conditions (living alone, with partner, children, etc.), diabetes type and duration, glycemic control, body mass index (BMI), history of previous foot ulcers and amputations, foot deformities, index foot ulcer characteristics (site, area, depth, duration, infection grade), number of active ulcers, use of tobacco, peripheral artery disease (toe pressure, TcPO₂), and neuropathy (assessed with Ipswitch Touch Test and Vibratip).

Categorical data will be summarized as n (%).

Continues data will be summarized as mean (standard deviation).

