6.1.8 SENSITIVITY ANALYSES

The primary outcome will be analyzed on the ITT data set, per protocol dataset, and ITT dataset using multiple regression as a sensitivity analysis to test the robustness of the results. Multiple imputation will also be used as a sensitivity analysis for the primary outcome (see point 6.2).

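### SAP 6.1.2 mislabels three Cox covariates as stratification factors and no specified model contains study site; in SAP 6.1.1 backward selection over 20–22 candidates with few non-healed participants can drop ulcer area

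*SAP*

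**What the plan says.** SAP 2.2: "The randomization will be stratified for study site and ulcer area", the area being cut at 1 cm². The Protocol (Methods) agrees: "The randomization will be stratified for ulcer size", and by study center.

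SAP 6.1.2 analyses time to healing with a "Cox proportional hazards model including stratification factors (ulcer area and depth at baseline, periphery artery disease and infection grade) initially".

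SAP 6.1.1 adds an adjusted ITT analysis of 12-week healing. The baseline variables of SAP 5.1 "will be included as candidates in a logistic multiple regression, using backward selection and a p-value of 0.10 as cut-off for removal". These include the "index foot ulcer characteristics (site, area, depth, duration, infection grade"; the word site there means where the ulcer lies on the foot, not the study site. The same section says "Participants for whom the 12 week observation is missing will be categorized as" not healed. SAP 6.1.8 gives the role of this model: "ITT dataset using multiple regression as a sensitivity analysis to test the robustness of the results".

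SAP 2.3 plans on the basis that "the proportion of healed ulcers after 12 weeks treatment is estimated to 90% with sealed shoe or TCC". It aims for 150 participants, with a fallback stop once the endpoint has been observed in 112.

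**The concern.** An analyst reading SAP 6.1.2 cannot tell whether to follow the label (the randomisation strata) or the list in brackets, and the word *initially* leaves the final Cox model open. Study site, a true stratification factor, appears in neither named model. Ulcer area, the other one, can be removed from the logistic model at p>0.10.

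The logistic model also has far more candidates than the expected number of non-healed participants can support. The starting model may have no finite fit, and when it does fit, the standard error may be too small. SAP 6.1.1 gives no rule for non-convergence, so a remedy would be chosen after the data are seen. At stake is how much a planned robustness check is worth, and whether the Cox analysis is fully prespecified.

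**Working it through.** **Texts side by side**

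| Place | Study site | Ulcer area | Depth, arterial disease, infection grade |
|---|---|---|---|
| Randomisation (Protocol; SAP 2.2) | stratifies | stratifies (1 cm²) | do not stratify |
| Cox model (SAP 6.1.2) | absent | included | included, labelled as strata |
| Logistic model (SAP 6.1.1) | absent | removable | removable |

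The covariates of other adjusted secondary analyses (SAP 6.1.2) and of the multiple imputation (SAP 6.2) are not named.

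**The plan's sample size.** With 90% in both arms, a 10-point margin, one-sided 0.05 and 80% power, the usual formula is n = (1.645+0.842)² × 2×0.9×0.1 / 0.1² ≈ 111.3, so 112 *per arm* (224 in total). The SAP's 112 in total is not reproduced. That is a separate matter; below I use the numbers the SAP intends to recruit. At 224 there would be 22.4 non-healed with none missing, still only 22.4/22 to 22.4/20 = 1.02–1.12 per candidate.

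**Candidates (SAP 6.1.1 with 5.1).** Sex, age, education, living conditions (4); diabetes type, duration, HbA1c, BMI (4); prior ulcers, prior amputations, deformities (3); ulcer location, area, depth, duration, infection (5); number of ulcers, tobacco, arterial disease, neuropathy (4). Total 20, or 22 if toe pressure and TcPO₂, and the two neuropathy tests, count separately. Multi-category variables would add parameters.

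**Non-healed participants** (10% missing is an assumption; the documents give no rate)

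- None missing: 112×0.10 = 11.2; 150×0.10 = 15. Per candidate: 0.51–0.56 and 0.68–0.75.
- Fallback, 10% missing: 112 counts *observed* endpoints, so 112/0.9 ≈ 124 are randomised; 12.4 + 11.2 = 23.6, about 24. Per candidate: 1.07–1.18.
- N=150, 10% missing: 150×(0.10+0.90×0.10) = 28.5. Per candidate: 1.30–1.43.

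**Logistic simulation.** 2,000 trials per setting; 20 or 22 noise covariates, half binary (prevalence 0.5 or 0.3) and half normal; equal healing in both arms; treatment always kept.

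| Randomised | Missing | Starting model unfittable | SE after selection too small by |
|---|---|---|---|
| 112 | 0 | 17–36% | 17–25% |
| 150 | 0 | 2–11% | 9–16% |
| 112 | 10% | at most 2% | 16–17% |
| 150 | 10% | at most 0.2% | 9–12% |

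Smaller runs (600–1,000 trials, 20 candidates) add:

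- N=112, 5% missing: 112×(0.05+0.95×0.10) = 16.2 non-healed; unfittable in 2–3%.
- N=124, 10% missing: 0%.
- Healing 90% vs 80%, none missing: N=112 gives 5.6+11.2 = 16.8 non-healed, unfittable in about 2–4%; N=150 gives 7.5+15 = 22.5, at most 0.1%.

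Coverage after selection is about 91–95% two-sided and 91–96% for the one-sided bound of SAP 3.1. At 90% vs 80% the one-sided bound covers 94–96%, no worse than the crude OR in the same runs.

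The full model without selection has an SE 27–55% too small (none missing) or 11–32% (10% missing). The cause is therefore too few non-healed per candidate together with selection, not selection alone. The crude OR ranges from 8% too small to 1% too large.

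If healing differs by ulcer-area stratum (assumed 95% vs 85%), selection drops ulcer area in 44% of fitted trials (N=112) or 34–36% (N=150); at 97% vs 83%, in 20–22% or 9–10%.

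**Cox simulation.** Assumed 3, 5 or 8 sites. Mean type I error without site is 5.2% (site log-hazard SD 0.3) or 4.0% (SD 0.6). With 4,000 trials per null setting, the simulation error of one setting is √(0.05×0.95/4000) = 0.34 points, so 5.2% shows no inflation. At HR 1.3 or 1.6, stratifying by site instead of omitting it changes power by −1 to +3 points (SD 0.3) or +5 to +9 points (SD 0.6).

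**The case against.** The Cox model can be run exactly as listed, and depth, arterial disease and infection are sensible prognostic covariates. Leaving site out does not raise type I error. At the planned 90% in both arms there is no difference to detect and so no power to lose. Part of the power gain at SD 0.6 reflects the lower type I error without site. All this stands: the Cox part is mainly a correction of wording.

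On the logistic model, the 17–36% failure rate needs the fallback size, no missing outcome at all and equal 90% healing. Failure falls quickly with a few missing outcomes, or at the non-inferiority limit of 90% vs 80%. The SE ratio also overstates the harm somewhat: in one rerun, a median-based ratio gave 0.85 instead of 0.82 (N=112) and 0.93 instead of 0.86 (N=150). These points stand too, and they limit the size of the issue.

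It can also be said that a short model gives up a check for imbalance in arterial disease, infection or depth. That is a fair cost. But a model that starts with about 0.5–1.4 non-healed per candidate cannot carry out that check reliably. The contradiction in labels, the absence of site and the possible removal of ulcer area are not answered by any of this.

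**Conclusion.** The point holds, as minor to moderate. The inconsistency between SAP 2.2 and 6.1.2 is certain from the text. So is the absence of study site from both named models. The candidate and non-healed counts follow from the SAP's own inputs, apart from the assumed missing rate. The simulation figures rest on noise covariates, treatment being kept, and assumed numbers of sites and site effects, none of which the documents give.

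A reader might infer more, and the documents do not support it:

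- *That the primary result is at risk.* The crude ITT and per-protocol analyses use no selection, and SAP 6.1.8 gives the regression a sensitivity role.
- *That omitting site makes the Cox test invalid.* Type I error stays at or below about 5%; power is lost only if sites differ clearly in healing rate.
- *That the adjusted model will usually fail.* Failure is common only in one corner of the plausible range, and the one-sided bound shows no visible loss at 90% vs 80%.
- *That site is excluded from every analysis.* For the imputation and the other adjusted secondary analyses the covariates are simply unnamed.

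**What to change.** SAP 6.1.2: name study site and the 1 cm² ulcer-area stratum as the stratification factors and put both in the Cox model, with site as strata or as a covariate. Relabel depth, peripheral artery disease and infection grade as prespecified prognostic covariates. Delete *initially*.

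SAP 6.1.1: replace the backward selection with one short prespecified logistic model that always keeps treatment, the ulcer-area stratum and study site. Pool small sites by a rule based on size only, fixed before unblinding; the documents give no site numbers, so the trial team must set the threshold. Name in advance a penalised-likelihood method, such as Firth, for sparse data or separation.

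The need for that method is real. With three assumed sites and none missing, ordinary maximum likelihood for the short model failed in 19–37% of simulated trials (N=112) and 8–24% (N=150). Firth fits with at most five sites, or with small sites pooled, converged in all 44×2,000 = 88,000 trials, with two-sided coverage 94.5–96.3% and one-sided 94.7–96.4%. These runs had no treatment effect; the 90% vs 80% boundary was not tested. With eight unpooled sites 0.4–2.8% did not converge, hence the pooling rule.

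Cost: SAP wording only. Downsides: a pooling rule is needed, the other baseline variables are no longer screened, and a site-stratified Cox test may be slightly liberal (about 5.2–5.6% in simulation).
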